### **21.3 Analysis Populations**

The primary population for efficacy and safety will consist of the modified ITT population, i.e., patients who receive at least one dose of study drug and have any follow-up data. A per protocol

efficacy population will consist of all patients who fulfill the inclusion/exclusion criteria and receive at least 4 weeks of treatment with study drug as well as at least 90% of the planned radiation therapy.

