Study Design	
This will be an open label, uncontrolled Phase 1b/2 trial in patients with newly diagnosed GBM who have recovered from complete or partial surgical resection. All patients will be treated with PLX3397 in addition to standard-of-care combination radiation therapy (RT) plus temozolomide (TMZ) followed by adjuvant TMZ. During Phase 1b dose escalation, two PLX3397 administration schedules, 7 days/week vs. 5 days/week (M-F) will be explored. During Phase 2, patients will be treated with the RP2D.
 
There are 4 sequential periods: 1-week PLX3397 monotherapy; 6-week PLX3397/RT/TMZ combination therapy; 4-week recovery; and, PLX3397/TMZ adjuvant therapy. PLX3397 will be administered twice daily either 7 days/week or 5 days/week (Monday through Friday) starting 1 week prior to the initiation of RT and will continue twice daily either 7 days/week or 5 days/week (Monday through Friday) during the 6-week course of RT.
 
Phase 1b PLX3397 dose and schedule cohorts are:
 
  
 Cohort	Combination PLX3397/RT/TMZ	Adjuvant PLX3397/TMZ	
 
 PLX3397 Dose	PLX3397 Schedule	PLX3397 Dose	PLX3397 Schedule	
   
 -2	600 mg/day	5 days/week (M-F)b	800 mg/dayb	7 days/week	
 
 -1	600 mg/day	7 days/weeka	600 mg/daya 800 mg/dayb	7 days/week	
 
 1	800 mg/day	7 days/weeka 5 days/week (M-F)b	1000 mg/dayb	7 days/week	
 
 2	1000 mg/day	5 days/week (M-F)b	1200 mg/dayb	7 days/week	
  
 
a Amendment 1. b Amendment 2.
 
For combination PLX3397/RT/TMZ PLX3397 treatment, dose escalation to the next highest cohort may occur after all patients have completed the 11-week DLT-observation period (i.e., 1-week PLX3397 monotherapy; 6-week PLX3397/RT/TMZ combination therapy; 4-week recovery). For adjuvant PLX3397/TMZ PLX3397 treatment, dose escalation to the next highest cohort may occur after all patients have completed an 8-week DLT-observation period (i.e., 2 cycles of adjuvant treatment). For patients participating in Phase 1b, intra and inter patient dose escalation to a higher dose level/schedule will be permitted after that dose level/schedule has been established to be safe.
 
The RT schedule will be once 5 days/week (Monday through Friday) for 6 weeks (total radiation dose of 60 Gy using either conformal or IMRT planning). Oral temozolomide will be administered once daily (7 days per week) for the duration of RT. Four weeks after the completion of the course of RT, patients will be started on once-daily adjuvant temozolomide (Day 1-5 of a 28 day cycle) for up to 12 cycles as long as there is no disease progression or unacceptable toxicity and PLX3397 twice daily (28 days of a 28 day cycle) for as long as there is no disease progression or unacceptable toxicity. After discontinuation of study drug, patients will continue to be followed for OS every 6 months.
				Cohort	Combination PLX3397/RT/TMZ		Adjuvant PLX3397/TMZ		PLX3397 Dose	PLX3397 Schedule	PLX3397 Dose	PLX3397 Schedule	-2	600 mg/day	5 days/week (M-F) b	800 mg/day b	7 days/week	-1	600 mg/day	7 days/week a	600 mg/day a 800 mg/day b	7 days/week	1	800 mg/day	7 days/week a 5 days/week (M-F) b	1000 mg/day b	7 days/week	2	1000 mg/day	5 days/week (M-F) b	1200 mg/day b	7 days/week

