--	--

	
12. Women of child-bearing potential who are pregnant or breast feeding.
 
13. At Screening QTcF <math>\geq 450</math> msec for males and <math>\geq 470</math> msec for females.

Dosage and Regimen	
Study drug will be administered orally using a capsule formulation (200 mg per capsule). The total daily dose of PLX3397 will be divided and administered BID. For an uneven number of capsules, the larger dose will be administered in the morning.
 
For Phase 1b PLX3397 dose and schedule cohorts and escalation, see Study Design (above).
 
The Phase 2 portion of the study will use the RP2D selected from the Phase 1b portion of the study.
 
As a part of standard of care, patients will receive the following:
 
 
• 60 Gy of radiation therapy Monday-Friday for a total of 30 radiation treatments over approximately 6 weeks.
 
• Temozolomide 75 mg/m^2 PO once daily for approximately 6 weeks beginning the first day of RT until RT end, followed by adjuvant treatment at a dose of 150 mg/m^2 once daily on Days 1-5 of the first 28 day cycle after completion of radiation therapy (start of Cycle 3). The dose can be escalated to 200 mg/m^2 if the non-hematologic toxicity is Grade <math>\leq 2</math> (except for alopecia, nausea, and vomiting), absolute neutrophil count (ANC) is <math>\geq 1.5 \times 10^9/L</math>, and the platelet count is <math>\geq 100 \times 10^9/L</math>.
 
• During the 4-week break after the completion of RT, neither temozolamide nor study drug will be administered.
 

Safety and Tolerability Assessments	
Physical examinations, vital signs, 12-lead ECGs, adverse events, hematology, and serum chemistry will be used to assess safety and tolerability.
 
As this is an open label study, ongoing safety will be continuously and rigorously monitored by the Sponsor. Additionally, biweekly teleconferences are planned to review in detail the safety across all study sites. Prior to dose escalation in the Phase 1b portion, safety data will be collated and reviewed by the Sponsor and study sites by teleconference.

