#### 21.4 Efficacy Analysis

Response to treatment will be evaluated using the Response Assessment in Neuro-Oncology (RANO) criteria (Wen 2010). The response criteria are summarized in Attachment 3. All patients who are eligible for efficacy analyses will be evaluable for PFS, calculated for each subject as the number of days from the first day of treatment (C1D1) to the date of the first documented disease progression or date of death, whichever occurs first. The Kaplan-Meier method will be used to estimate the median PFS.

Statistical modeling will be used to match the experimental group to the RTOG 0525 historical group for expected prognosis based on both clinical and molecular factors, importantly the level of MGMT methylation in the tumor tissue.

For each subject with a response to therapy, duration of response will be calculated. The duration of response is defined as number of days from the date of initial response to the date of first documented disease progression or death, whichever occurs first. The Kaplan-Meier method will be used to estimate median duration of response. In the event no disease progression or death is documented prior to study termination, analysis cutoff, or the start of confounding anticancer therapy, PFS and duration of response will be censored at the date of last evaluable tumor assessments. The median duration will be compared to the historical control PFS of 5.5 months. The secondary endpoint of OS will be analyzed in a similar fashion.

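### The per-protocol set is selected on treatment received up to about day 44, but its PFS is counted from C1D1, so its median is biased upward relative to the mITT by between 0 and about 1.4 months

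*Combined protocol and SAP*

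**What the plan says.** Section 21.3 states: "The primary population for efficacy and safety will consist of the modified ITT population", defined as "patients who receive at least one dose of study drug and have any follow-up data". It then names a per-protocol efficacy population: patients who meet the eligibility criteria and "receive at least 4 weeks of treatment with study drug as well as at least 90% of the planned radiation therapy".

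Section 21.4 gives a single PFS definition. It opens with "All patients who are eligible for efficacy analyses will be evaluable for PFS" and measures time "from the first day of treatment (C1D1) to the date of the first documented disease progression or date of death". No other time origin, landmark or delayed entry is given for the per-protocol set.

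The timing comes from the synopsis. PLX3397 is given "starting 1 week prior to the initiation of RT", and RT is planned "for a total of 30 radiation treatments over approximately 6 weeks", Monday to Friday. The synopsis (Study Procedures) also makes the scan taken about 3 to 4 weeks after RT the baseline for judging progression. Neither trial flow chart schedules an MRI between Screening and C3D1.

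**The concern.** Membership of the set depends on what happens after the clock has started. A patient cannot receive 27 fractions without surviving to the 27th, so every per-protocol patient carries about six weeks in which death was impossible by construction. That time still counts as PFS. This is immortal time.

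The trial is uncontrolled, and its Phase 2 question is median PFS against a fixed 5.5 months. No concurrent arm undergoes the same selection, so the bias does not cancel. Nothing in Section 21.4 prevents the per-protocol median from being set beside 5.5 months. If it were, an inactive drug could look better than the benchmark.

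**Working it through.** The plan states no expected per-protocol median, so there is no figure of its own to reproduce. The check takes a true median of 5.5 months and asks what the selection rule does to it.

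**Inputs**
- Benchmark median 5.5 months; one-sided level 0.10; about 31 evaluable of 44 patients (Section 21.2).
- RT from C1D8, 30 fractions, five per week (synopsis). 90% is 0.9 × 30 = 27 fractions.
- Assumptions: RT starts on a Monday and is not interrupted; every patient with an event before the qualifying date leaves the set; 18 months of follow-up in the simulated tests.

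**Qualifying date.** Fractions 1 to 25 take five weeks, days 8 to 40. Fraction 26 falls on day 43 and fraction 27 on day 44, which is 43 days after C1D1. So t₀ = 43/30.44 = 1.41 months. The 4-week drug condition is reached earlier (28/30.44 = 0.92 months) and does not set the date.

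**Shift in the median.** Let the hazard before t₀ be a fraction g of the later hazard λ, with the all-patient median held at 5.5 months. The per-protocol median m solves H(m) = ln 2 + H(t₀), where H is the cumulative hazard. The extra hazard g·λ·t₀ is made up at rate λ, so

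m = 5.5 + g × 1.41.

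The same medians result if the low hazard lasts until week 11.

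**If the set were tested against 5.5 months.** The plan assigns it no test. As an illustration, use a one-sample log-rank statistic, Z = (O − E)/√E, rejecting below −1.28. E is the sum over patients of (ln 2/5.5) × time at risk. Start from 31 to 44 enrolled, drop those with an event before t₀, and keep the C1D1 origin. For the rejection rates, the reduced hazard applies to the first 43 days.

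| Early hazard as fraction of later (g) | Per-protocol median, months | Rejection under a true 5.5-month median |
|---|---|---|
| 1 (constant hazard) | 5.5 + 1.41 = 6.91 | about 31–38% |
| 0.5 | 5.5 + 0.71 = 6.21 | about 12–14% |
| 0.25 | 5.5 + 0.35 = 5.85 | about 6% |
| 0.1 | 5.5 + 0.14 = 5.64 | not computed |
| 0 | 5.50 | not computed |

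In the constant-hazard row, 1 − exp(−(ln 2/5.5) × 1.41) = 16% of patients leave the set, about 7 of 44. In that row, all patients together reject 8–9% of the time, and the per-protocol set with delayed entry at t₀ also rejects 8–9%. The excess therefore comes from the time origin.

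**By share excluded.** If 1%, 2%, 5% or 10% of patients leave because of an early event, with a 5.5-month exponential, the shift is 0.08, 0.16, 0.41 or 0.84 months.

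**The case against.** The strongest reply is that this window may contain few events. Progression is judged against the post-RT scan and no MRI is scheduled before it, so PFS events before about week 11 are essentially deaths or clinical deterioration. That points to the lower rows of the table. This stands: 6.9 months is the upper end, not the expected value, and the documents do not allow a choice within the range.

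The mITT is primary, and no test, alpha or decision is attached to the per-protocol set. This also stands. Section 21.4 plans to match patients to the historical group on prognosis, but matching on baseline factors does not remove selection on treatment received later.

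Several stronger readings are tempting and are not supported:

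- *All early progressors are removed.* The rule concerns treatment received. A patient with early clinical progression who still reaches both thresholds stays in, with an early event. The guarantee is strict only for survival.
- *Type I error is 34–44%.* That takes 30 to 44 patients as the size of the per-protocol set. About 44 is the whole planned number, and the 16% exclusion that produces the bias would leave about 37.
- *The bias stays large when early events are rare.* Lowering the early hazard while leaving the later hazard at ln 2/5.5 gives 37–38% rejection per protocol, against 20–29% in all patients. The true all-patient median is then about 6.2 to 6.6 months, so this is not a null calculation.
- *The 5.5-month benchmark is unselected.* The documents give neither its time origin nor its selection rules. The bias can be stated relative to the mITT, but not settled against the benchmark.
- *The primary result is affected, because the 31 evaluable patients are the per-protocol set.* Section 21.2 does not tie evaluability to either population, but Section 21.3 makes the mITT primary.

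**Conclusion.** The defect is real and confined to a supportive analysis; it is minor. Sections 21.3 and 21.4 together bias the per-protocol median PFS upward relative to the mITT. With a true median of 5.5 months the shift lies between 0 and about 1.4 months.

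The upper end needs a constant hazard from C1D1 and the exclusion of every patient with an event before about day 44. Patients who progress early but stay in the set make it smaller. A test against 5.5 months, which the plan does not specify, would reject about 31–38% of the time at that end, about 12–14% if the early hazard were half the later one, and below the nominal 10% if it were a quarter. The direction is certain if any patient leaves the set because of an early event; the size cannot be fixed from the documents. The primary mITT analysis does not carry this rule.

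**What to change.** Add to Sections 21.3 and 21.4:

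1. Only mITT PFS, counted from C1D1, is compared with the 5.5-month benchmark.
2. Per-protocol PFS is labelled supportive and uses delayed entry: each patient is at risk from the date both treatment conditions are met, and observed and expected events are counted from that date. Alternatively, present it as a landmark analysis from the end of RT.

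This takes a few lines of text and no new data, since dosing and fraction dates are needed anyway to define the set. The per-protocol result will look slightly less favourable. A landmark median is not directly comparable with 5.5 months. For a landmark at day 44 with g = 0.5, for example, it would be 6.21 − 1.41 = 4.80 months from the landmark although the all-patient median from C1D1 is 5.5. It should not be printed beside the benchmark without that explanation.

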#### 21.4 Efficacy Analysis

Response to treatment will be evaluated using the Response Assessment in Neuro-Oncology (RANO) criteria (Wen 2010). The response criteria are summarized in Attachment 3. All patients who are eligible for efficacy analyses will be evaluable for PFS, calculated for each subject as the number of days from the first day of treatment (C1D1) to the date of the first documented disease progression or date of death, whichever occurs first. The Kaplan-Meier method will be used to estimate the median PFS.

Statistical modeling will be used to match the experimental group to the RTOG 0525 historical group for expected prognosis based on both clinical and molecular factors, importantly the level of MGMT methylation in the tumor tissue.

For each subject with a response to therapy, duration of response will be calculated. The duration of response is defined as number of days from the date of initial response to the date of first documented disease progression or death, whichever occurs first. The Kaplan-Meier method will be used to estimate median duration of response. In the event no disease progression or death is documented prior to study termination, analysis cutoff, or the start of confounding anticancer therapy, PFS and duration of response will be censored at the date of last evaluable tumor assessments. The median duration will be compared to the historical control PFS of 5.5 months. The secondary endpoint of OS will be analyzed in a similar fashion.

Additional secondary analysis of efficacy will include patient-specific biomathematical modeling of tumor growth (Baldock 2013) to allow quantification of the degree of deflection of the tumor off of its growth curve related to the therapy (Neal 2013a; Neal 2013b; Adair 2014). The patient-specific model will be tuned to the pre-treatment MRIs. The degree of deflection of the tumor off of its growth curve will be measured as Days Gained and as Radial Treatment Response as in (Neal 2013a; Neal 2013b; Adair 2014). Briefly, patient-specific simulations of predicted tumor growth will be compared with followup MRIs in terms of a temporal delay of imageable tumor growth (Days Gained) or as a delay of tumor growth in terms of size (Radial Treatment Response). These metrics will be correlated with PFS and OS through correlative and Kaplan-Meier analyses to connect treatment response with outcomes. In addition, relationships between treatment response, PFS, PD biomarkers, and tissue prognostic markers will be explored.

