Study Procedures	
After providing informed consent, patients will undergo screening for eligibility to participate in the study. Screening will start within 3 weeks prior to PLX3397 dosing. Following recovery from surgical resection, patients who meet inclusion/exclusion criteria will start study drug on the morning of any Monday through Friday (Cycle 1 Day 1; C1D1). This visit should occur between 3 weeks and 5 weeks after surgery. Patients will continue to dose study drug twice daily either 7 days/week or 5 days/week (Monday through Friday) and return to the clinic for evaluation on C1D8, the day they initiate radiation therapy plus temozolomide.
 
For the Phase 1b portion of the study, a blood sample will be obtained pre-dose on C1D1 for the baseline PK. On C1D8 and on C1D15, blood samples will be obtained pre-dose and 1, 2, 4, and 6 hours post-dose to estimate PLX3397 PK. Patients will return to the clinic on Cycle 2 Day 1 (C2D1) for evaluation. If PLX3397 has been well tolerated and there has been no clinical evidence of disease progression, continued dosing will be permitted. Patients will be monitored for response and disease progression with MRI brain scans every 2 cycles, with the brain scan obtained approximately 3-4 weeks after the completion of RT serving as the baseline scan for determination of progression.
 
For Phase 1b PLX3397 dose and schedule cohorts and escalation, see Study Design (above.)
 
For the Phase 2 portion of the study, patients will be treated with PLX3397 at the RP2D level.
 
For both phases, patients will be monitored throughout the study for adverse reactions to the study drug and/or study procedures.
 
Hematology assessments (i.e., CBC, differential count, and platelet count) will be performed weekly starting with C1D1 and continuing through the first week of the Recovery Period (RPD8). Serum chemistry assessments will be performed at Screening, C1D1, C1D15, C2D1, and C2D22 (completion of RT). For the adjuvant treatment period, assessments will be made on the day of treatment initiation (C3D1), C3D22, and D22 of each subsequent cycle, and at study completion or upon early withdrawal. A serum pregnancy test will be completed at Screening for applicable patients.
 
Blood pressure, respiratory rate, pulse rate and temperature will be measured at each study visit. A standard 12-lead electrocardiogram (ECG) will be performed for each patient at Screening, C1D1, C2D1, and study completion.
 
A complete physical examination will be performed for each patient at Screening. A neurological exam and a symptom-directed physical exam will be completed on each subsequent visit while continuing study therapy, and at study completion or upon early withdrawal. Patients will also complete the MD Anderson Symptom Inventory-Brain Tumor Module at the time points noted in the Trial Flow Chart, and Karnofsky performance status will be recorded as noted.
 
A surgical paraffin tumor block (or at least 20 unstained slides) will be identified during Screening for subsequent shipment to the central pathologist. Blood samples for circulating CSF-1, biomarkers of kinase inhibition and myeloid cell recruitment will be obtained pre-dose on C1D1, C1D8, C2D1, and C3D1. CD14/16 mononuclear cell counts will be obtained pre-dose on C1D1 and C1D8.
 
Commencing on 01 October 2017, patient visits, clinical laboratory testing, and MRI brain scans will be performed approximately every 12 weeks (please refer to the TRIAL FLOW CHART – Phase 2 for details).

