## 10.0 DESIGN

### 10.1 Description

This will be an open label, uncontrolled Phase 1b/2 trial in patients with newly diagnosed GBM who have recovered from complete or partial surgical resection. All patients will be treated with PLX3397 in addition to standard-of-care combination radiation therapy (RT) plus temozolomide (TMZ) followed by adjuvant TMZ. During Phase 1b dose escalation, two PLX3397 administration schedules, 7 days/week vs. 5 days/week (M-F) will be explored. During Phase 2, patients will be treated with the RP2D.

There are 4 sequential periods: 1-week PLX3397 monotherapy; 6-week PLX3397/RT/TMZ combination therapy; 4-week recovery; and, PLX3397/TMZ adjuvant therapy. PLX3397 will be administered twice daily either 7 days/week or 5 days/week (Monday through Friday) starting 1 week prior to the initiation of RT and will continue twice daily either 7 days/week or 5 days/week (Monday through Friday) during the 6-week course of RT.

Phase 1b PLX3397 dose and schedule cohorts are shown in [Table 2](#).

A detailed Trial Flow Chart is available in [Section 6.0](#), and procedures by study day are provided in [Section 13.0](#).

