### **21.2 Sample Size and Power**

For the primary endpoint of median PFS, based on a one-sided log rank test with a significance level of 0.1 and power of 80%, 22 events (death or progression) in approximately 31 patients would be required to detect a 50% relative hazard reduction in progression-free survival due to the addition of PLX3397 compared to the recent historical control median PFS of 5.5 months (RTOG 0525). Assuming a ~30% rate of non-evaluability, approximately 37 patients are planned to be enrolled in the Phase 2 portion of the study, which when combined with the 7 patients treated at that dose level in the Phase 1 portion of the study will yield approximately 44 patients.

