- d) Stable non-enhancing (T2/FLAIR) lesions on same or lower dose of corticosteroids compared to baseline scan. In the event that the corticosteroid dose has been increased, the last scan considered to show stable disease will be the scan obtained when the corticosteroid dose was equivalent to the baseline dose.
- e) Stable clinically.

**Progressive Disease** (defined by any of the following):

- a) >25% increase in sum of the products of perpendicular diameters (bi-dimensional measurements) of enhancing lesions (over baseline if no decrease) on stable or increasing doses of corticosteroids. and/or
- b) Significant increase in T2/FLAIR non-enhancing lesion on stable or increasing doses of corticosteroids compared to baseline scan or best response following initiation of therapy, not due to co-morbid events (radiation therapy, demyelination, ischemic injury, infection, seizures, postoperative changes, or other treatment effects).
- c) Any new lesion.
- d) Clear clinical deterioration not attributable to other causes apart from the tumor (e.g., seizures, medication side effects, complications of therapy, cerebrovascular events, infection, etc.). The definition of clinical deterioration is left to the discretion of the treating physician, but it is recommended that a decrease in 20% of KPS or from any baseline to 50% or less be considered, unless attributable to comorbid events.
- e) Failure to return for evaluation due to death or deteriorating condition.

**Assessment of Response** (Efficacy)

Timing of the Evaluation of Response: Assessment of response will begin with the previous MRI. All scans are to be compared to the smallest measurement scan to date.

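### PFS is counted from C1D1, but the plan does not say when the clock of its 5.5-month historical benchmark starts, so the error rate of the comparison is not established

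*Combined protocol and SAP*

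**What the plan says.** Section 21.4 calculates PFS "as the number of days from the first day of treatment (C1D1) to the date of the first documented disease progression", or to death if that comes first. Of the C1D1 visit, the synopsis (Study Procedures) states: "This visit should occur between 3 weeks and 5 weeks after surgery". Section 8.2 places C1D1 one week before radiotherapy, followed by six weeks of RT and a four-week recovery. The synopsis describes MRI monitoring "with the brain scan obtained approximately 3-4 weeks after the completion of RT serving as the baseline scan for determination of progression". Both flow charts schedule MRI at Screening and next at C3D1, with none between.

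Section 10.1 begins: "This will be an open label, uncontrolled Phase 1b/2 trial". The comparator is therefore external. Section 21.2 sizes the trial to detect a 50% relative hazard reduction "compared to the recent historical control median PFS of 5.5 months (RTOG 0525". Section 21.4 plans modelling to match patients to the historical group on expected prognosis. The synopsis (PD Parameters) allows the 5.5 months to be adjusted for MGMT status.

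On the comparator scan, Attachment 3 says "Assessment of response will begin with the previous MRI" and "All scans are to be compared to the smallest measurement scan to date". Its list of progression events also includes clinical deterioration and "Failure to return for evaluation due to death or deteriorating condition".

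**The concern.** A single-arm comparison with a fixed median is valid only if both medians are measured from the same point by the same progression rule. Here the trial's side is defined. The benchmark's side is only a number and a study name: no section states its time origin, scan schedule or progression baseline, and the reference list has no entry for it. The planned adjustments deal with who the patients are, not with when their clocks start.

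If the clocks differ, the actual one-sided error is not the stated 0.10, and it could be higher or lower. The choice of comparator scan also matters, because it sets event dates in the primary endpoint.

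**Working it through.** **1. The plan's own figure.** Inputs from Section 21.2: one-sided alpha 0.10 (z = 1.2816), power 80% (z = 0.8416), 22 events, 5.5 months. The plan does not name a one-sample statistic. With a square-root-transformed one-sample log-rank test, expected events are E = [(1.2816 + 0.8416) / (2(1 − √HR))]² and observed events are HR × E.

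- HR 5.5/8.25 = 0.667: E = 33.5, events 22.3. This reproduces 22.
- HR 0.5 (median 5.5/0.5 = 11.0 months if exponential): E = 13.1, events 6.6. Other one-sample variants give up to 10, and two-sample formulas 38 or 41.
- HR 5.5/8 = 0.69 (the 8 months of Section 10.5): E = 38.6, events 26.5.

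So 22 events fits a median 50% longer, not a hazard 50% lower. The patient number is consistent: 31/0.7 = 44.3, against 44 stated.

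**2. Clock offsets** (30.4375 days per month), from the protocol calendar:

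- surgery: 21 to 35 days before C1D1 = −0.69 to −1.15 months
- RT start: 7 days after = +0.23
- post-RT scan: 7 weeks plus 3-4 weeks = 70 to 77 days after = +2.30 to +2.53
- C3D1 with its ±7-day window: up to 84 days = +2.76

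Placing the benchmark's origin anywhere in this range is an assumption.

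**3. From offset to median.** Suppose the benchmark starts s months after C1D1, in patients event-free at that point, and a share q of trial patients has an event before s. With an inactive drug, the median on the C1D1 clock is s + 5.5 × log2((1 − q)/0.5). It equals 5.5 when q = 1 − 2^(−s/5.5), which is 25.2% at s = 2.30 and 27.3% at s = 2.53. These are also the shares that a constant hazard with median 5.5 produces by those times. A late origin therefore favours the drug only if early events are rarer than that. The documents give no value for q.

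**4. False positives.** Simulation of 40,000 runs per cell: 31 or 44 patients, uniform accrual over 6 or 18 months, analysis at the 22nd event, rejection if (E − O)/√E > 1.2816 against an exponential with median 5.5. Early events are spread evenly over (0, s). The ranges also cover repeat runs.

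| Benchmark origin | Inactive-drug median from C1D1 (months) | False positives |
|---|---|---|
| C1D1 | 5.5 | about 8% |
| Surgery, no benchmark event before C1D1 | 5.5 − 0.69 = 4.81 to 5.5 − 1.15 = 4.35 | 0.3-2% |
| RT start, no event in week 1 | 5.5 + 0.23 = 5.73 | 10-12% |
| Week 11, q = 20% | 2.53 + 5.5 × log2(1.6) = 6.26 | 18-25% |
| Week 11, q = 27% | 2.53 + 5.5 × log2(1.46) = 5.53 | 8-9% |

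A Kaplan-Meier version (lower one-sided 90% limit of survival at 5.5 months above one half) gives a similar picture: 8-9% aligned, 1-3% from surgery, 10-12% from RT start, and 14-24% at weeks 10-11 with q = 20%. With aligned clocks, power of the simulated test is 96% at HR 0.5 and about 65% at HR 0.69.

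**5. Comparator scan.** The synopsis names the post-RT scan as the progression baseline. Attachment 3 starts from the preceding MRI and uses the smallest scan to date, without saying whether the pre-RT Screening scan counts. If it counts, the C3D1 scan could itself be scored as progression. If it does not, Attachment 3 is a nadir rule applied after the synopsis baseline.

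**The case against.** The strongest reply is that no error has been shown. Starting PFS at first treatment is conventional and clearly defined, and whether the benchmark differs depends on a source outside the documents. This stands, and it limits the point to something missing that has to be supplied.

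Three stronger readings are tempting, and the documents do not support them.

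- A reader might infer that up to 2.5 months of PFS is credited to the drug. The figures of −1.15 to +2.5 months are assumed clock offsets, not shifts in the median. A gain of 2.5 months would need no early events at all, yet death, clinical deterioration and failure to return all count before the post-RT scan.
- A reader might infer a severely inflated error. Rates of 42-64% do appear in the simulation for a week-11 origin with a 10% early-event share, but that share has no source. The absence of MRI between Screening and C3D1 makes a low share plausible, not established.
- A reader might infer that the synopsis and Attachment 3 contradict each other. They can be read together, as a post-RT baseline followed by a nadir rule. What is missing is the cross-reference.

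It is also fair to object that the simulated statistic is my assumption: aligned, it gives about 8% error, not 10%. The percentages show direction and rough size and do not describe the sponsor's exact test. None of this supplies the benchmark's origin, and the planned adjustments do not either.

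**Conclusion.** The point holds as a gap in the definition of the primary comparison. A mismatch between the clocks is possible, not shown, and of unknown sign. A surgery origin would make the test conservative, an RT-start origin would change little, and an origin near week 11 would inflate the error only below the early-event threshold derived above. These sizes rest on exponential PFS, a one-sample log-rank test at 22 events, and an early-event share that the documents do not give. Until the origin is stated, the nominal one-sided 0.10 is unsupported in either direction.

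The scan wording in Attachment 3 is a secondary ambiguity that needs clarifying. The conflict between Section 21.2 (11 months if exponential) and Section 10.5 (about 8 months) is also secondary, but it stands on the documents alone.

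**What to change.** Before the primary PFS analysis, with the date recorded because the trial is open label:

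- Establish the time origin and progression baseline of the 5.5-month figure, and express the null median on the C1D1 clock in the modified ITT population, so that early deaths and progressions count.
- If the benchmark is defined only from a later point, add a landmark comparison in patients event-free at that point. Label it as a different estimand and report it beside C1D1-based PFS.
- If the origin cannot be established, report the comparison over the plausible origins (surgery, C1D1, RT start, post-RT scan) and do not claim a one-sided 0.10 error.
- State in Attachment 3 which scan is the progression baseline, consistent with the synopsis.
- Reconcile the HR 0.5 and 8-month targets, and restate power for the one adopted under the re-expressed null.

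The cost is SAP text and analysis work, with no new patient data. The null median may become longer (6.26 months in the week-11, 20% illustration) and the stated power lower. Without the RTOG 0525 detail, only a range can be reported, and it may not settle the question.
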